All Cohort 2 study volunteers will undergo the screening visit with the following tests which are identical to Cohort 1 (Table 2), a medical and laboratory examination to determine study eligibility. Qualifying volunteers will be invited for the full study at the Metabolic Clinical Research Unit as inpatients. Subject criteria are the same as in Cohort 1. Subjects will be studied with 7-14 days between admissions and complete the entire study (Cohort 2) within a 12-week time window to prevent the variability in outdoor environmental temperatures and potentially body weight which will confound the study.

During six 1-day stays at the NIH Hatfield Clinical Research Center, study volunteers will undergo daily BMR measurements (up to 4 hours) in a metabolic chamber while exposed to temperatures of 27.0°C. Chamber conditions and assays are exactly as described for Cohort 1 (Table 5).

Table 6. Medications in Cohort 2

Treatment	Dose	Route	Minimum washout
Placebo		PO	None
Caffeine	300 mg	PO	3 days
Qsymia	topiramate 92 mg CR phentermine 15 mg	PO	4 days

Phentermine HCl	37.5 mg	PO	4 days
Topiramate	200 mg	PO	4 days
Naltrexone	100 mg	PO	? Days

III.2-3 Protocol design, Cohort 3 - This Cohort has completed enrollment

Cohort 3 is a randomized, single-blind, placebo controlled study, with the quantifier of BAT activity blinded to the four different interventions. Volunteers will undergo up to four experiments to study the effects of mirabegron on BMR and BAT activity.

All Cohort 3 study volunteers will undergo the screening visit with the following tests which are identical to Cohorts 1 and 2 (Table 2), including a medical and laboratory examination to determine study eligibility. Qualifying volunteers will be invited for the full study at the Metabolic Clinical Research Unit as inpatients. Subject criteria are the same as in Cohorts 1 and 2. At least 48 hours will separate each of the study days, and all 4 study visits will be completed within a 12-week time window to prevent the variability in outdoor environmental temperatures and potentially body weight which will confound the study.

[figure not shown]

Figure 2. Schematic depicting the testing parameters and procedures for Cohort 3.

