Study volunteers will be provided with an isocaloric dinner meal the evening prior to metabolic testing. It will consist of the following macronutrient distribution: 55% carbohydrate, 15% protein, and 30% fat, as recommended by the American Dietetic Association. A late night snack high in carbohydrates and protein will also be provided due to the prolonged fasting period the following day. Volunteers will be expected to consume their snack by midnight and then fast until testing is complete, approximately 16 hours. Then, he may resume a regular diet.

Body composition

A DXA scan (iDXA, GE Healthcare, Madison WI) will be performed at either Day 1 or 2 of the inpatient study stage. With this technique, one can determine total and

regional body fat and lean soft tissue masses, bone mineral content and density. DXA produces photons at two different energy levels, 40 and 70 KeV. The photons pass through tissues and attenuate at rates related to elemental composition. Bone mineral, with highly attenuating calcium and phosphorous, is readily distinguished from soft tissues. The different elemental profiles of fat and bone-mineral free lean components allows for the analysis of soft tissue fat content, so that bone mineral, fat, and bone mineral fat-free lean components may be resolved.

Environmental questionnaire

On Day 1, each subject will answer general questions about their typical thermal environment, such as the number of hours/day usually spent outside, clothing typically worn, environmental temperature at work and at home, and level of physical activity.

PET/CT (Cohort 3 only)

A PET/CT scan is the current standard for measuring BAT activation in humans. Study volunteers in Cohort 3 will be scanned following each stay in the metabolic chamber. At 13:00, a 5mCi dose of ¹⁸FDG will be given intravenously to volunteers through the blood port of the metabolic chamber. At the end of the study (14:00), study volunteers exit the metabolic chamber and are then transported via a wheelchair to Nuclear Medicine Department of the NIH Clinical Center and a PET/CT scan will be performed on the Siemens mCT scanner. The PET/CT scan will expose the study volunteer to about 1.25 rem of total effective radiation exposure.

MRI (Cohort 3 only)

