
Continuous EKG (up to 6 hours per day)

A portable Holter monitor will be used to collect heart rate variability in the standard three-lead configuration (4 hypoallergenic disposable EKG electrodes). No known risks have been reported.

Tympanic and surface temperature measurements. (up to 6 hours per day)

A non-invasive tympanic thermometer (PRO4000 by Braun) will be used measured every 30 minutes by the study subjects after trained by our study staff. Wireless surface patches (VitalSense, Mini Mitter, Bend OR) will be used to measure the skin temperature by a portable receiver positioned close to the body. No known side-effect has been reported.

Surface Electromyography sensors with accelerometers (up to 6 hours per day)

The solid-state sensors, each measuring 1.5x1x0.6 inch, pick up electric signals generated by the muscle fibers, which are transmitted wirelessly to the computer. Sensors will be taped with thin hypoallergenic double-sided tape to the specific skin sites, and pose no risk to the subjects.

Infrared thermography

We know of no significant risks from taking pictures with a camera in the infrared range.

Urine collection (up to 6 hours per day)

Besides the inconveniences that can reasonably be expected as a result of 4-5 hour urine collection during specific time periods, there is no health risk of this procedure.

DXA Scan (1 test)

The use of DXA scan apparatus may cause some minimal discomfort in claustrophobic subjects and may cause some minimal back pain in a small minority of the individuals.

PET/CT (4 scans)

The PET/CT scanner apparatus may cause some discomfort in claustrophobic patients and from lying in a supine position for an extended period of time. Volunteers may also experience minor discomfort and/or bruising at the site of the intravenous injection of the PET radiotracer.

MRI (4 scans)

The MRI scanner apparatus may cause some discomfort in claustrophobic patients and from lying in a supine position for an extended period of time.

Use of fiducial markers (4 times)

The placement of these markers (up to 16) is not expected to cause any pain to the subjects. Volunteers may experience some skin irritation at the site(s) of placement. They will be adhered to the skin surface.

Radiation Safety

The radiation exposure of a DXA scan is less than 1 mrem per session. A normal individual is exposed to 300 mrem/year from natural sources (background exposure).

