Each PET/CT scan will use 5 mCi of ^{18}FDG . The radiation exposure of the PET/CT is an effective dose of 0.83 rem, 3.5 rem/year for 4 PET/CT scans, which is below the guideline of 5 rem per year allowed for research subjects by the NIH Radiation Safety Committee. A typical radiation dosage from a chest x-ray is 20 mrem.

The fiducial markers will contain 1 μCi of Na-22. This adds 0.000085 rem per PET to the current radiation dosage. The effective dose for this study remains 3.5 rem/year.

Blood drawing

The placement of intravenous needles may cause transient pain, and rare infection or bruising at the insertion site.

Fasting over time

The discomfort of fasting daily from midnight until 13:00 (16:30 for Cohort 3) of next day can be difficult for some subjects. There is no known long term harm to the subjects as overall energy balance (dietary intake = energy expenditure) is preserved.

III.7 Adverse events

Adverse events, non-compliance both serious or continuing, protocol deviations both major and minor, as well as unanticipated problems are defined & described by the NIH Office of Human Subjects Research Protection policy #801, and will be reported in accordance with this policy.

Serious adverse events

The PI is responsible for summarizing all serious adverse events and adverse events at least possibly related to the research procedure and interventions at the time of Continuing Review. All deaths that have occurred among study participants since the previous review will be summarized at the time of continuing review. A serious adverse event is any experience that:

1. Results in death;
2. Is life threatening;
3. Results in hospitalization or prolongs hospitalization;
4. Results in persistent or significant disability/incapacity;
5. Results in congenital anomaly/birth defect; or
6. Results in a condition, which in the judgment of the investigator represents a significant hazard.

Clinical Monitoring

Study procedures will be subject to audits and/or monitoring visits to ensure compliance with the protocol and applicable regulatory requirements consistent with the NIDDK quality assurance program plan. Audit and/or monitoring visit results will be reported to the Principal Investigator for further reporting as appropriate. Study documents and pertinent hospital or clinical records will be reviewed to verify that the conduct of the study is consistent with the protocol plan.

Data and Safety Monitoring Plan

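### The protocol gives two effective doses, about 1.25 rem and 0.83 rem, for the same 5 mCi FDG PET/CT, and its statement that four scans stay below 5 rem depends on which is right

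*Combined protocol and SAP*

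**What the plan says.** Only Cohort 3 has PET/CT. Two places in the protocol give its radiation dose.

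- **III.5 Methods, PET/CT (Cohort 3 only).** The procedure begins "At 13:00, a 5mCi dose of" FDG and the paragraph ends: "The PET/CT scan will expose the study volunteer to about 1.25 rem of total effective radiation exposure".
- **III.6 Possible Risks and Hazards, Radiation Safety.** The activity is the same: "Each PET/CT scan will use 5 mCi of" FDG. The dose is not: "The radiation exposure of the PET/CT is an effective dose of 0.83 rem, 3.5 rem/year for 4 PET/CT scans". The section then sets this total against the annual limit and concludes: "which is below the guideline of 5 rem per year allowed for research subjects".

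Radiation Safety also covers two small sources. For DXA: "The radiation exposure of a DXA scan is less than 1 mrem per session". For the fiducial markers: "This adds 0.000085 rem per PET to the current radiation dosage". It then repeats 3.5 rem/year as the study total. The MRI paragraph in III.5 says that MRI adds no radiation.

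III.2-3 requires that "all 4 study visits will be completed within a 12-week time window", so a subject's four scans fall within one year. Subjects with detectable brown fat after cold exposure have four scans. Those without have two: the cold day and the 200 mg day. III.4 excludes volunteers whose radiation exposure in the past year would take them over research limits.

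**The concern.** Both figures stand in current text and both describe one PET/CT with 5 mCi of FDG, so they cannot both be right. The per-scan dose is the basis for the statement that a four-scan subject stays below the annual guideline. That statement has a comfortable margin on one figure and none on the other.

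The same dose is needed to apply the prior-exposure exclusion in III.4. Whether earlier exposure would take a volunteer over the limit depends on how much this study adds. At the higher figure, a four-scan subject has no room for other research exposure in that year.

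**Working it through.** **Inputs**

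- Dose per PET/CT: about 1.25 rem (III.5) or 0.83 rem (III.6)
- Scans per subject with detectable brown fat: 4 (III.2-3, III.6)
- Stated total: 3.5 rem/year; guideline: 5 rem/year (III.6)
- DXA: under 0.001 rem, one session; markers: 0.000085 rem per PET (III.6)

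**1. Can the stated total be reproduced?** Total = scans × dose per scan.

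- From 0.83: 4 × 0.83 = 3.32 rem. The stated 3.5 is 0.18 rem higher (0.18 / 3.32 = 5.4%).
- Rounding of 0.83 to two decimals: 4 × 0.825 = 3.30 to 4 × 0.835 = 3.34, which does not reach 3.5.
- Adding DXA and markers: 0.001 + 4 × 0.000085 = 0.00134 rem at most, giving 3.321 rem. If the marker dose were per marker, with 16 markers, the total would be 3.32 + 0.001 + 4 × 16 × 0.000085 = 3.326 rem.
- From 1.25: two scans give 2.50, three give 3.75 and four give 5.00. No whole number of scans gives 3.5.
- Back-calculation: 3.5 / 4 = 0.875 rem per scan, which is neither stated figure.

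So 3.5 is not reproduced exactly. It lies close to four scans at 0.83 and may be that total rounded up. It does not fit 1.25.

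**2. Comparison with the 5 rem guideline**

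| Basis | Four scans (rem) | Margin under 5 rem |
|---|---|---|
| 0.83 per scan | 3.32 | 5 − 3.32 = 1.68 |
| 3.5 as stated | 3.5 | 5 − 3.5 = 1.5 |
| 1.25 per scan | 5.00 | 5 − 5.00 = 0 |

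If 1.25 is itself rounded to two decimals, the four-scan total lies between 4 × 1.245 = 4.98 and 4 × 1.255 = 5.02 rem, on either side of the guideline.

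**3. Size of the conflict and who is affected**

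- Per scan: 1.25 / 0.83 = 1.51, so one figure is 51% higher than the other.
- Two-scan subjects: 2 × 0.83 = 1.66 or 2 × 1.25 = 2.50 rem, well below 5 on either figure.
- Planned four-scan subjects (III.1, power calculation): 28 of the 42 who have Study Day A at full size, or 12 of 18 if the study stops after the interim analysis. These are plans; the documents do not say which applied.

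**4. Can the two figures be reconciled?**

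- 1.25 rem as the total for all scans would contradict both 0.83 per scan and 3.5 per year.
- The word about in III.5 cannot stretch 0.83 to 1.25.
- Neither place says that its figure leaves out the CT part; both refer to the PET/CT.
- DXA, markers and MRI add far too little.

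**The case against.** The best counter-argument is that the documents show which figure governs. Radiation Safety is the only section that adds up the dose and compares it with a limit, and its total, stated twice, fits about 0.83 and not 1.25. The Methods figure is one approximate sentence that no calculation uses. On that reading 1.25 is a stray number and the conclusion about the guideline is sound. This is a reasonable inference and probably the likelier one, but the documents do not confirm it, and the Methods text would still need correcting.

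Other points on that side:

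- **No breach.** Four times an approximate 1.25 could fall on either side of 5 rem. This stands: at 1.25 the statement is unsupported, not shown to be false.
- **The 3.32 against 3.5 gap is harmless.** This stands. The stated total errs on the cautious side, and the gap carries no weight as a safety matter.
- **The exclusion has a limit.** III.4 gives no number, but read with III.6 the limit is 5 rem per year. This stands. What remains uncertain is the study's own contribution, which is the same discrepancy.
- **Little is left to change.** Cohort 3 enrollment is complete. This limits the practical effect, but completed enrollment does not prove that all scans are done, and the safety record remains inconsistent.
- **Unseen sources.** The consent pages and the radiation committee's records are not available here, so the approved dose may be documented elsewhere. That is a reason to ask, and it does not reconcile the protocol text.

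**Conclusion.** The concern holds, as a minor one. III.5 and III.6 give per-scan effective doses that differ by 51% for the same procedure, and at least one must be wrong. If 0.83 rem is correct, a four-scan subject receives 3.32 rem and the comparison with the guideline stands with about 1.7 rem to spare. If about 1.25 rem is correct, the total is about 5.0 rem within 12 weeks and the claim of being below the guideline is not supported.

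The internal evidence favours 0.83 without settling it. The totals assume four scans with equal doses and take the two stated figures at face value. No overexposure is shown, two-scan subjects are not in question, and no endpoint, sample size or analysis is affected.

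**What to change.** 1. Ask the site's radiation safety staff to confirm the effective dose of one PET/CT at 5 mCi FDG.
2. Use that single figure in III.5 (PET/CT) and III.6 (Radiation Safety).
3. Restate the four-scan total from it, noting any upward rounding, and restate the comparison with 5 rem.
4. Use the restated total when applying the III.4 prior-exposure exclusion, if any scans remain.
5. Only if about 1.25 rem is confirmed, check whether any four-scan subject had other research exposure in the same year.

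The cost is one enquiry and edits in two places. Procedures, recruitment and analysis do not change. Step 5 is the only added work, and it is conditional.

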Appendix I

The following survey will appear on a custom-programmed iPAD App, in the identical appearance as follows:

Comfort Questionnaire

Date of survey (MM/DD/YYYY): _ _ / _ _ / _ _ _ _

Time of survey (HH:MM): _ _ : _ _ AM PM (circle AM or PM)

How do you feel about the room temperature?

Very hot ————— Very cold

How do you feel about the room humidity?

Very humid ————— Very Dry

How do you feel about the room air flow?

Very drafty ————— No air movement at all

Are you sweating?

Profusely ————— Not at all

Are you shivering?

Constantly ————— Not at all

How hungry do you feel?

I am not hungry at all ————— I have never been more hungry

Other parameters (noted by investigator at time of VAS report; this section is not shared with subject):

Current Chamber Temperature: _____

Current Relative Humidity: _____

Previous day Chamber Temperature: _____

Current Outdoor Temperature: _____

Previous day Outdoor temperature (high): _____

Previous day Outdoor temperature (low): _____

Patient room temperature: _____

Other comments:
